Dosage/Dose Regimen: Multiple treatments may be administered in this study. Request for retreatment can occur at scheduled clinic visits, scheduled telephone visits, or between scheduled visits. If the request is made at a scheduled clinic visit, then that visit will also become the qualification for retreatment visit, otherwise a qualification for retreatment clinic visit should be conducted within approximately 1 to 2 weeks of the patient/parent/caregiver request. (Note that those patients who qualified for retreatment in the preceding study 191622-120, at which point they exited, do not need to be requalified to receive their first retreatment in this study).

BOTOX®

The qualification for retreatment criteria are:

- patient/parent/caregiver requests retreatment
- patient has a total of at least 2 daytime urinary incontinence episodes over the 2-day diary collection period
- at least 12 weeks has elapsed since their previous study treatment
- · patient has not experienced a serious treatment-related adverse event at any time

Treatment will be administered within 4 weeks (28 days) after a patient qualifies for retreatment. Retreatment can be administered up to 48 weeks since enrollment on day 1.

All study treatments will be administered once all "day of treatment criteria" are fulfilled (see Section 5.9.1). Treatment will be administered via cystoscopy (rigid or flexible cystoscope) as 20 intradetrusor injections of 0.5 mL each evenly distributed, sparing the trigone. Administration will be under general anesthesia for all patients < 12 years of age. For patients 12 years and older, administration can be under local anesthesia (with or without sedation), or general anesthesia. Precautions for latex sensitivity or allergy will be taken, in accordance with local site practice.

Randomization/Stratification: No randomization or stratification will be performed in this long-term extension study.

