## 3. Study Design

This is a multicenter, double-blind, long-term extension study to the preceding study, 191622-120. Patients will roll over directly from the preceding study; the exit visit of study 191622-120 is also the entry visit (day 1) for Study 191622-121 (patients exit Study 191622-120 once they have qualified for retreatment, or at week 48 if they never qualified).

Patients can receive multiple double-blind treatments of 50, 100, or 200 U BOTOX (not to exceed 6 U/kg) in the extension study once they qualify for retreatment (for the first retreatment this qualification may have occurred in the preceding study). The dose received at any given treatment will be determined by the investigator based on the response to the preceding blinded treatment. The investigator can elect to keep the dose the same or increase the dose compared to the preceding treatment (if it is deemed a decrease in dose is warranted, the patient would be exited from the study). The actual dose received remains blinded (unless the patient is requested to exit the study via the IVRS, as described at the end of Section 5.5, or until the interim analysis has been reported as described in Section 7.7). The study medication will be administered via cystoscopy as 20 evenly spaced intradetrusor injections of 0.5 mL each, sparing the trigone.

Following any treatment, patients will have posttreatment follow-up clinic visits at weeks 2, 6, and 12, and then alternating telephone and clinic visits every 6 weeks thereafter until they qualify for further retreatment or exit the study. Request for retreatment can occur at any scheduled clinic or telephone visit, or between scheduled visits. If a request occurs at a scheduled clinic visit, this then becomes a qualification for retreatment visit, otherwise a qualification for retreatment clinic visit should occur within approximately 1 to 2 weeks of request. Patients exit the study once 48 weeks have elapsed since entry on day 1 and at least 12 weeks follow-up since their last study treatment has occurred (exit will therefore be between 48 and 60 weeks since study entry on day 1; the latter being for patients who received retreatment at week 48).

The efficacy measure of key interest is daytime urinary incontinence episodes, and the key timepoint is week 6 after each treatment.

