1.1 Primary Study Objectives and Design

The objective of study 191622-121 is to evaluate the long-term safety and efficacy of BOTOX for the treatment of urinary incontinence due to NDO in patients 5 to 17 years of age who have not been adequately managed with anticholinergic therapy.

This is a long-term extension study to the preceding study, 191622-120. Patients will roll over directly from the preceding study; the exit visit of study 191622-120 is also the entry visit for study 191622-121. Patients exit study 191622-120 once they have qualified for retreatment or at week 48 if they never qualified. For the first retreatment in study 191622-121, the qualification may have occurred in study 191622-120.

In this study, patients can receive multiple injections of the following doses:

- 50 units (U) BOTOX (not to exceed 6 U/kg)
- 100 U BOTOX (not to exceed 6 U/kg)
- 200 U BOTOX (not to exceed 6 U/kg)

In order to ensure that the upper dosing limit of 6 U/kg is not exceeded, the actual dose administered is adjusted based on patient weight, if necessary.

The dose received at any given treatment will be determined by the investigator based on the response to the preceding blinded treatment. The investigator can elect to keep the dose the same or increase the dose compared to the preceding treatment. If it is deemed a decrease in dose is warranted, the patient would be exited from the study. The actual dose received remains blinded unless the patient is requested to exit the study via the IVRS, as described at the end of Section 5.5 of the protocol or until the interim analysis of this study has been reported.

Patients in this study are evaluated at scheduled visits at 2, 6, and 12 weeks after each retreatment (week 2, 6 and 12 visits). After week 12 visit (12 weeks from the re-treatment), there are alternating telephone and clinic visits every 6 weeks until they qualify for further retreatment or exit the study. Request for retreatment can occur at any scheduled clinic or telephone visit, or between scheduled visits. If a request occurs at a scheduled clinic visit, this then becomes a qualification for retreatment visit, otherwise a qualification for retreatment clinic visit should occur within approximately 1 to 2 weeks of request.

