2.3 Data Conventions

The following data conventions will be applied to all analyses.

- Baseline and study baseline are used interchangeably throughout this document. They both refer to baseline information collected at the start of study 191622-120.
- In general, metric systems will be used (e.g., kilograms (kg) and centimeters (cm)) and clinical laboratory data will be presented with the Standard International (SI) units.
- The variance for Kaplan-Meier estimates will be calculated using Greenwood's formula.

- Descriptive statistics for continuous variables include the sample size (n), mean, SD, median, minimum (min), first quartile (Q1), third quartile (Q3), and maximum (max).
- Summary statistics for categorical variables include the sample size (n), frequency count and percent.
- The Medical Dictionary for Regulatory Activities (MedDRA) dictionary will be used to code all adverse events (AEs) and medical histories.
- World Health Organization Drug Dictionary Enhanced (WHO DDE) preferred name and MedDRA will be used to code all medications.
- Cumulative study duration from Day 1 (first injection date in preceding study 191622-120) will be calculated as:

Study day in study = visit date - day 1 date + 1.

 Cycle duration for a given Treatment X (i.e., Xth injection cycle where X > 1)will be calculated as:

Study day of cycle X = visit date - day 1 of Treatment X + 1.

- The algorithm presented in Table 3, together with the rules below will be used to impute incomplete or missing dates for adverse events and medications as follows:
 - (a) AE start dates will be imputed as the minimum of the following:
 - initial imputed date, where target date = first study drug injection date if the AE started in study 191622-120; exit day in study 191622-120 if the AE started in study 191622-121.
 - complete end date
 - (b) Medication start dates will be imputed as the minimum of the following:
 - initial imputed date, where target date = first study drug injection date 1 if the medication started in study 191622-120; exit day in study 191622-120 if the medication started in sudy 191622-121.
 - complete end date
 - (c) AE and Medication end dates will be imputed as the minimum of the following:

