6.2 Adverse Events

Adverse events (AEs) will be coded by system organ class and preferred term using the Medical Dictionary for Regulatory Activities (MedDRA).

Pre-treatment AEs are AEs that have start date on or after the signing of consent form and prior to the first BOTOX injection.

An AE will be considered a cycle 1 treatment-emergent adverse event (TEAE) if it fulfills one of the conditions below:

• the start date of the AE is on or after the 1st BOTOX injection and prior to the date of the 2nd BOTOX injection

• the AE started before the 1st BOTOX injection and increased in severity or became serious during the cycle (from date of 1st BOTOX injection to the day before the 2nd injection).

For subsequent cycles (cycle's number > 1) an AE is considered a TEAE in the current cycle if it fulfills one of the conditions listed below.

- the AE start date is within the cycle i.e., it is on or after the date of the cycle injection and prior to the date of the next injection
- the AE has increased in severity or became serious during the current cycle

The incidences of TEAEs will be summarized by BOTOX treatment cycle.

The number and percentage of patients reporting TEAE in each treatment group will be tabulated by descending percentage in any group, by system organ class and preferred term, and further categorized by severity and causal relationship to the study drug and study drug injection procedure. If more than 1 AE is coded to the same patient, the patient will be counted only once for that preferred term using the greatest severity for the summarization by severity and causal relationship.

The number and percentage of patients who have treatment-emergent serious adverse events (TESAE) will be summarized by system organ class, preferred term and treatment group. Similar summary will be presented for patients with TEAE leading to discontinuation from the study. In addition, separate patient listings will be generated for deaths, SAEs, and TEAEs leading to study discontinuation.

In addition, the incidence of TEAEs, SAEs, study drug/study injection procedure related TEAEs, deaths and TEAEs leading to study discontinuation will be reported for the overall study period.

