All the summaries discussed above will be based on all AEs observed during the entire cycle. Since the design of this study allows patients to request/receive retreatment from week 12 (day 84) onward, an additional summary showing the number and percentage of patients with TEAEs by preferred term and treatment group in descending order of incidence will be presented for the TEAE observed prior to or on day 84 after each injection cycle. This will allow for a comparison across dose groups for the same duration of time (ie, since patients can request retreatment from week 12 onwards, patients remain in a cycle for varying time periods). Therefore this analysis provides a more direct comparison across dose groups.

In addition, the number and percentage of patients who have a treatment-emergent UTI during the first 2 weeks (14 days), the first 12 weeks (84 days), and during the overall treatment cycle will be presented by the treatment received in each treatment cycle.

The number of UTI events per patient year will be summarized for the six month prior to screening and for each BOTOX treatment cycle. The number of UTI events per patient year, for the BOTOX treatment cycle, is defined as follows: (The sum of all the patients UTI events)/ (The sum of all the patients duration in years during the BOTOX treatment cycle). The number of UTI events per patient year for the 6-months prior to screening is similarly defined. All patients will be included in these analyses irrespective of whether they experienced a UTI or not.

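### By-cycle tables of serious, related, graded and discontinuation AEs use whole-cycle percentages although later cycles are observed for less time, and no fixed-window version is planned

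*SAP*

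**What the plan says.** SAP 6.2 tabulates treatment-emergent adverse events (TEAEs) by cycle as numbers and percentages of patients, including breakdowns by severity and by relationship to drug or procedure. It adds that "patients who have treatment-emergent serious adverse events (TESAE) will be summarized by system organ class, preferred term and treatment group", with a similar table for TEAEs leading to discontinuation. It then fixes the window for all of these: "All the summaries discussed above will be based on all AEs observed during the entire cycle".

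The same section acknowledges that time in a cycle varies between patients and adds summaries limited to a fixed time:

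- a day-84 table of all TEAEs by preferred term, whose stated purpose is comparison across dose groups;
- UTI percentages at 14 days, at 84 days and over the whole cycle.

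The only rate per unit time is UTI events per patient-year, with denominator "The sum of all the patients duration in years during the BOTOX treatment cycle". Serious, related, graded and discontinuation TEAEs have neither a fixed window nor a rate. SAP 6.1.1 summarises cycle duration separately but does not use it as a denominator.

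Cycle 1 spans both studies. It begins at the first injection in study 191622-120 ("Cumulative study duration from Day 1 (first injection date in preceding study 191622-120) will be calculated as"), and an event belongs to it if "the start date of the AE is on or after the 1st BOTOX injection and prior to the date of the 2nd BOTOX injection". On leaving the first study, SAP 1.1 says: "Patients exit study 191622-120 once they have qualified for retreatment or at week 48 if they never qualified". In the extension, "Retreatment can be administered up to 48 weeks since enrollment on day 1" (Protocol Summary), and Protocol 3 says "Patients exit the study once 48 weeks have elapsed since entry on day 1 and at least 12 weeks follow-up" have passed since the last treatment.

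**The concern.** Long-term safety over repeated treatment is a study objective (Protocol 2.1). Protocol 1 already summarises the adult programme in these terms, saying that the incidence of the common urological events did not increase with repeat treatment. Readers will put the same question to the by-cycle columns here.

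A percentage of patients with at least one event depends on how long they were watched. If the design gives later cycles less time, the percentage can fall across cycles with no change in risk, and a real rise could be hidden. The SAP accepts this reasoning for comparing doses. It gives no reason for not applying it to comparing cycles, or for leaving out serious and related events.

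**Working it through.** **Inputs from the documents.** At most 48 weeks in study 191622-120 (SAP 1.1); at least 12 weeks between treatments (Protocol 5.10.1); last injection no later than week 48 of the extension (Protocol 5.9.1); injection within 4 weeks of qualifying (Protocol 5.9.1); exit at the later of week 48 and 12 weeks after the last injection (Protocol 3).

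**Assumptions not in the documents.** Event rate, retreatment intervals, the lag d within the permitted 0 to 4 weeks, and no dropout.

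**1. The plan's own figure.** Exit = max(48, last injection + 12), so the latest exit is 48 + 12 = 60 weeks. This reproduces the stated 48 to 60 weeks.

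**2. Longest possible cycles.** Cycle 1: 48 + 48 = 96 weeks. For k ≥ 2 the earliest injection in the extension is t = d + (k − 2)(12 + d), and the longest cycle is max(48, t + 12) − t.

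| Lag d | C1 | C2 | C3 | C4 | C5 |
|---|---|---|---|---|---|
| 0 weeks | 96 | 48 | 36 | 24 | 12 |
| 2 weeks | 96 | 46 | 32 | 18 | 12 |

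A sixth cycle is possible only with no lag at all. At a constant 0.2 events per patient-year, 1 − exp(−0.2 × weeks/52) at the no-lag ceilings gives 30.9, 16.9, 12.9, 8.8 and 4.5%. These are bounds, not expected values.

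**3. Realistic lengths.** Simulated whole-cycle percentages at a constant 0.2 per patient-year:

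| Retreatment timing (assumed) | C1 | C2 | C3 | C4 | C1/C4 |
|---|---|---|---|---|---|
| Lognormal, median 20 weeks, no lag | 8.8 | 8.3 | 6.5 | 5.1 | 1.7 |
| Lognormal, median 40 weeks, no lag | 15.7 | 11.4 | 6.6 | 5.0 | 3.1 |
| Lognormal, median 40 weeks, 2-week lag | 16.3 | 11.6 | 6.3 | 4.7 | 3.5 |
| Exponential tail after week 12, median 18 weeks, 2-week lag | 8.0 | 8.3 | 7.3 | 4.8 | 1.7 |
| Exponential tail, median 26 weeks, 2-week lag | 12.0 | 10.7 | 7.2 | 4.6 | 2.6 |
| Exponential tail, median 36 weeks, 2-week lag | 15.4 | 11.6 | 6.8 | 4.6 | 3.3 |

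The lognormal runs use log-SD 0.6, within-patient correlation 0.5, a 12-week minimum and 200,000 patients; the exponential runs use 100,000. A common 84-day window gives 1 − exp(−0.2 × 12/52) = 4.5% in every cycle, so the trend disappears.

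**4. Shape of the risk.** With 0.4 per patient-year for 12 weeks and 0.1 afterwards (lognormal, no lag), cycle 1 to cycle 4 goes from 10.9 to 9.1% at median 20 weeks (1.2-fold) and from 14.4 to 9.0% at median 40 weeks (1.6-fold). If every event falls within 12 weeks of injection (exponential tail, median 26 weeks), cycles 1 to 4 give 4.6, 4.6, 4.5 and 4.5%: no trend.

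**5. What a flat column could hide.** In the median-26 case, mean cycle length falls from 33.9 weeks (C1) to 12.3 weeks (C4). For cycle 4 also to show 12.0%, the rate would have to be about −ln(1 − 0.12) × 52/12.3 = 0.54 per patient-year, or 0.54/0.2 = 2.7 times the cycle 1 rate. This treats every fourth cycle as having the mean length.

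**6. How many children.** With lognormal median 40 weeks and a 2-week lag, about 9% reach cycle 4. That is 7 of 78 (SAP 1.1.1) to 9 of 100 (Protocol 7.6), with 9 × 0.047 ≈ 0.4 children expected to have an event. At median 20 weeks about half reach cycle 4.

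**The case against.** The strongest reply is that the fall needs risk to persist after week 12. That is least natural for drug- or procedure-related events, and no document gives an event rate. This stands: the size is conditional and may be nil for some tables.

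The SAP also gives readers more than the by-cycle percentages. It reports the incidence of TEAEs, SAEs, related TEAEs, deaths and discontinuations over the whole study period, lists SAEs and discontinuations by patient, and summarises cycle duration by dose group. The day-84 preferred-term table counts serious and related events, though it does not identify them. All of this limits the harm, but none of it gives a like-for-like comparison of serious or related events between cycles.

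Numbers also matter. Where the fall is steepest, very few children reach cycle 4; where cycle 4 is well populated, the fall is under twofold. The study is descriptive, with no hypothesis tests (Protocol 7.3), so the issue is how the tables will be read, not a faulty test.

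Three stronger readings are tempting, and the documents do not support them:

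- **A roughly sevenfold fall (30.9% to 4.5%) is to be expected.** That would give every child the longest possible cycle. Ninety-six weeks applies only to a child who reaches week 48 of the first study without qualifying and is then not retreated before week 48 of the extension.
- **Each successive cycle must look safer.** With short intervals, cycles 1 and 2 are about equal (8.8 and 8.3%, or 8.0 and 8.3%).
- **UTI rates and possible distant spread of toxin share the defect.** UTI already has 14- and 84-day percentages, and a distortion of its rate would need an assumed early clustering. SAP 6.2.1 does not say that distant-spread events are tabulated by cycle.

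**Conclusion.** The gap is real and modest. The TESAE, severity, relationship and discontinuation tables by cycle have no fixed-window version, while the design's own timing rules shorten later cycles. If risk continues after week 12, the percentages fall from cycle 1 to cycle 4 at unchanged risk by about 1.7- to 3.5-fold. This assumes a constant 0.2 events per patient-year, median intervals of 20 to 40 weeks and a lag of 0 to 2 weeks. Under the partly front-loaded risk assumed above it is about 1.2- to 1.6-fold, and with all events inside 12 weeks there is none. The direction follows from the design once risk persists; the size rests on assumptions the documents cannot settle.

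A fixed window does not make the cycles fully comparable. Children with a serious treatment-related event do not qualify for retreatment (Protocol 5.10.1), and those whose side effects warrant a lower dose leave the study (Protocol 5.5). Later cycles are therefore selected for tolerance. This acts in the same direction as shorter observation, and an 84-day cut does not correct it.

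**What to change.** In SAP 6.2:

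1. Add day-84 versions, by cycle and dose group, of the TESAE, related-TEAE, severity and discontinuation tables, using the filter the section already defines.
2. State that comparisons of these percentages across cycles rest primarily on the day-84 tables.
3. Keep the whole-cycle tables and show cycle duration beside them, so that late events stay visible and the reader can see how long each group was observed.
4. Add a note that later cycles exclude children with a serious treatment-related event and those who left because side effects warranted a lower dose, and that the day-84 cut does not remove this selection.

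No new data or methods are needed. The costs are more output pages and the loss of later events from the day-84 tables, which is why the whole-cycle tables must stay.

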6.2.1 Potential Distant Spread of Toxin Adverse Events (applicable to BOTOX® studies only)

To assess possible distant spread of toxin (PDSOT), 39 MedDRA preferred terms that may be associated with botulinum toxin effects have been identified. All AEs associated with PDSOT will be tabulated by SOC and treatment group; in addition, all PDSOT AEs will be listed by subject. The 39 terms are listed below.

MedDRA Preferred Terms Evaluated for Possible Distant Spread of Toxin

Cardiac Disorders

Bradycardia

Eve Disorders

Accommodation disorder

Diplopia

Extra ocular muscles paresis Eyelid function disorder

Eyelid ptosis

Pupillary reflex impaired

Vision blurred

Gastrointestinal Disorders

Constipation Dry mouth Dysphagia Ileus paralytic

Infections and Infestations

Botulism

Musculoskeletal and Connective Tissue Disorders

Muscular weakness

Nervous System Disorders

Bulbar palsy

Cranial nerve palsies multiple Cranial nerve paralysis

Dysarthria Facial paralysis Facial paresis Hyporeflexia Hypotonia

Paralysis Paresis cranial nerve Peripheral nerve palsy Peripheral paralysis Speech disorder

Vocal cord paralysis Vocal cord paresis

Renal and Urinary Disorders

Urinary retention

Respiratory, Thoracic and Mediastinal

Disorders

Aspiration

Diaphragmatic paralysis

Dysphonia Dyspnoea

Pneumonia aspiration Respiratory arrest Respiratory depression Respiratory failure

[figure not shown]
Reproductive System and Breast

[figure not shown]
Disorders

Pelvic floor muscle weakness

[figure not shown]
Note: The evaluation of events mapping to these terms will take into consideration the known mechanism of action of BOTOX, the temporal relationship of the event (time to onset of the AE), the duration of the event, any re-challenge information if applicable, confounding factors that may include co-morbidities, past medical history, concomitant medications and other non-specific constitutional symptoms of a subject. In accordance with this, certain

[figure not shown]
term may be excluded from the consideration for PDSOT AEs. For example, since BOTOX is injected into the urinary bladder for treatment of neurogenic overactive bladder, and since urinary retention is considered an expected localized effect, the preferred term 'urinary retention' will not be considered a PDSOT event for this study.

8. Health Outcomes Data Analyses

All analyses of health outcome variables are described in Section 5.

9. Interim Analyses

When all patients in study 191622-120 exit the study, there will be a data base lock (DBL) for study 191622-120 and a subsequent interim analysis for study 191622-121. A separate analysis plan is available with details of the interim analysis for study 191622-121. After this interim analysis the patients, investigator and Allergan staff will all be unblinded.

10. Analysis for US FDA

Not applicable.

11. Data Collected but not Analyzed

A patient's surgical history and female patients' birth control treatment during the study are collected in this study. No output will be generated for these data.

12. Deviations from Protocol

The number of patients that have reduction from baseline in daytime urinary incontinence episodes that meet certain threshold will not be analyzed using the non-normalized daytime rates of incontinence episodes. However, the non-normalized daily average frequency of daytime urinary incontinence episodes will be summarized.

13. References

14. Amendments

Following is a summary of content-oriented changes that were made to each section of the SAP, and a brief rationale for these changes. Minor editorial and document formatting revisions have not been summarized.

Amendment 1

Sections	Revision	Rationale
Section 2.1: Analysis Populations	Additional text included to clarify how participants are assigned to actual BOTOX treatment group based on actual dose administered.	To clarify how participants are assigned to actual BOTOX treatment group based on actual dose administered.
Section 2.3: Data Conventions	Modified imputation rules for completely missing or partial dates for adverse events and prior/concomitant medications	To reflect current company standard
Section 5: Efficacy Analyses	Subgroup analyses of key efficacy variable was removed	Only a subset of participants exit study 191622-120 and enroll in study 191622-121. These subgroup analyses are performed in study 191622-120
Section 6.2: Adverse Events	Section was re-written to reflect current company standard. For example updated definition of treatment-emergent adverse event	To reflect current company standard
Section 6.2.1: PDSOT adverse events	Paralysis flaccid was removed from the list of preferred terms. The preferred term "VII nerve paralysis" was replaced by "Facial paralysis"	Due to the update from MedDRA version 18.1 to version 19.0, Paralysis flaccid is being mapped to Paralysis, which is already included in the PDSOT list

Sections	Revision	Rationale
Section 9: Interim Analyses	Clarification that the planned interim analyses will have a separate interim analysis plan which will be a subset of analyses in the final analysis plan.	Full tables and listings are not required for the interim analysis. Intention is to support Final CSR of study 191622-120, providing key safety/efficacy data of repeat treatments for FDA submission.

Amendment 2

Sections	Revision	Rationale
Section 2.2 Analysis Visit Windows	Deleted the following text: "For laboratory and vital signs analysis, baseline refers to study baseline, i.e. the baseline information collected at the start of study 191622-121. This will be referred to as study baseline throughout this document."	To be consistent with all other assessments collected in this study, baseline now refers to information collected at the start of study 191622-120.
Section 2.3: Data Conventions	Added the following text: "Study baseline and baseline are used interchangeably throughout this document. They both refer to the baseline information collected at the start of study 191622-120.	To clarify at the beginning of this document that baseline refers to information collected at the start of study 191622-120.

ALLERGAN

Final Analysis Plan for 191622-121 Amendment 2

Date (DD/MMM/YYYY)/Time (PT)	Signed by:	Justification
